### **10.7. Will Identifiable Information be Released to Third Parties?**

The Principal Investigator will grant the NIH monitor(s), auditor(s), and regulatory authority(ies) access to the subject's original medical records for verification of data gathered on the CRFs and to audit the data collection process. The subject's confidentiality will be maintained and will not be made publicly available to the extent permitted by the applicable laws and regulations.

The investigators will not disclose to third parties any information about the participants without their expressed consent.

## **10.8. Sharing of Data/Samples with Other Researchers**

If sent to outside laboratories, samples will be coded and subject identifiers will be removed. The code number can be linked to a name only by the Principal Investigator and a designated Associate Investigator. If a biospecimen is sent to a clinical laboratory for testing, identifiers will not be removed and the result will become part of the NIH medical record.

## **10.9. Additional Features to Protect Confidentiality**

The protocol and associated data will be stored on the CTDB. The CTDB is a web-based application that supports flexible data capture and reporting. The system is hosted at the NIH in Bethesda, MD. It is accessible via the Internet through the NIH firewall, on both Mac and Windows based computers. An Oracle relational database is utilized to capture and secure data entered through the web interface. The following features allow for the safe and secure collection of research variables: an application firewall, data encryption and SSL certificates, HIPAA requirements, logical access controls, audit trails. Furthermore, only preauthorized users can access the CTDB. The Principal Investigator can determine the Associate Investigator's data access privileges.

## **11. ASSESSMENT OF RISK/BENEFIT RATIO**

The physical risks of phlebotomy, blood collection, muscle biopsy and ManNAc administration appear reasonable compared with the burden of the disease GNE myopathy. The benefits of this study relate to the future availability of a therapy for GNE myopathy. The benefit of such a treatment could be enormous for the community.

## 12. COLLECTION, MONITORING, ANALYSIS AND REPORTING OF ADVERSE EVENTS AND PROTOCOL DEVIATIONS

### 12.1. Adverse Events

AE definitions and classifications can be found below. Our safety monitoring plan is based on experience from the Phase 1 SAD trial of ManNAc (Section 3.5.3 and Appendix F), the 90-day toxicology studies in rat and dogs (See Appendix L) and the long-term toxicology studies in rats and dogs (Appendix M). We will monitor clinical laboratory tests including hemoglobin, liver function tests (See 5.2.2) and other clinical testing as medically indicated.

#### 12.1.1. Monitoring and Reporting of Adverse Events

Subjects will be evaluated and interviewed to identify AEs during the course of the study. AEs may also be identified through clinical examinations and laboratory tests. Events occurring after administration of the first dose of study medication will be recorded on the AE CRF. All AEs occurring from the time the informed consent is signed through the final dose of study drug must be documented, recorded and reported. After the final dose, all Grade  $\geq 2$  AEs at least possibly related to study drug will be followed to resolution.

A laboratory abnormality should be reported as an AE if it requires an intervention. Interventions include, but are not limited to, discontinuation of treatment, dose reduction/delay, additional assessments, or concomitant treatment. In addition, any medically important laboratory abnormality may be reported as an AE at the discretion of the investigator. This could include a laboratory result for which there is no intervention, but the abnormal value suggests disease or organ toxicity. The Investigator will evaluate all AEs with respect to Seriousness, Severity (intensity or grade), and Causality (relationship to study agent and relationship to research) according to the following guidelines.

The Medical Dictionary for Regulatory Activities (MedDRA) coding dictionary will be used for coding AEs.

The Investigator will grade the severity of each AE according to the “Common Terminology Criteria for Adverse Events (CTCAE)” in effect at the time of protocol activation which can be found at: [http://ctep.cancer.gov/protocolDevelopment/electronic\\_applications/ctc.htm](http://ctep.cancer.gov/protocolDevelopment/electronic_applications/ctc.htm)

Causality (likelihood that the event is related to the study agent) will be assessed considering the factors listed under the following categories:

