#### **3.8.2.2. 15-HG-0068 Open-Label Phase 2 Study (ClinicalTrials.gov Identifier: NCT02346461)**

There have only been no Serious Adverse Events observed as part of this Open-Label Phase 2 Study. The SRC review included safety through 24 months on all subjects. The reviewed safety information included adverse events (AEs), ECGs, vital signs, physical assessments and clinical laboratory data. Eight subjects remain on 6 grams twice daily. Four subjects have withdrawn consent, two of which discontinued due to gastrointestinal tolerability, another planning on getting pregnant and another was withdrawn due to noncompliance. AEs for the cohort from the latest SRC review are in [Appendix G](#). Due to 8 out of 12 subjects participating in this trial, demonstrated gastrointestinal tolerability issues or AEs related to ManNAc and 16% had tolerability issues significant enough to discontinue their participation, we have attempted to better understand the etiology of the decreased tolerability. The clinical manifestations together with PK evaluations, strongly suggest that unabsorbed ManNAc in the gastrointestinal tract is the likely cause. As discussed below in [Section 3.9.1](#), we believe absorption of ManNAc can be increased by 20% by giving the same daily dose of ManNAc (12 grams) divided three times (4 grams TID) instead of twice daily (6 grams BID).

One subject in the study had Grade 3 hypertriglyceridemia which was determined to be probably related to ManNAc. As higher triglycerides were also seen in toxicology studies (see [Table 10](#)), hypertriglyceridemia is a risk associated with ManNAc.

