**Figure 6. Dosing Escalation/De-escalation**

Table 6. Dose Escalation/De-escalation Rules	
Safety Profile*	Safety Review Committee Decisions*
No SAEs and Any number of CTCAE Grade 1 drug-related AEs or ≤ 1 CTCAE Grade 2 drug-related AE	Continue per protocol
2 CTCAE Grade 2 drug-related AEs	Continue per protocol, or study a lower dose § ,
≥ 3 CTCAE Grade 3 drug-related AEs	Study a lower dose § , or Withdraw the subject, and Convene SRC to evaluate the risk/benefit profile for dose escalation of other subjects
Any CTCAE Grade 4 AE; or ≥ 1 drug-related SAE Determination that the limit of safety and/or tolerability has been reached	Withdraw the subject, and Evaluate the risk/benefit profile in other subjects for dose escalations to or above the dose resulting in Grade 3 toxicity, and Discontinue study if 2 subjects develop the same Grade 3 toxicity or if any subject develops a Grade 4 toxicity

The safety decisions in this table apply only to safety and tolerability in an individual subject. If a decision is made that the dose escalation stopping criteria have been met, this does not preclude the use of the remaining subjects to evaluate the safety, PK, and PD effects of lower doses of ManNAc with the assessments described in this protocol.
 
*Note: Subjects from both Cohort A and Cohort B on 6,000 mg BID count toward the number of subjects experiencing toxicity.
 
§ Lower doses to study may include 4,500 mg BID, 3,000 mg BID or 2,000 mg BID depending on dose level where toxicity occurred.
	

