#### 7.2.2. Safety Evaluations

All safety data will be listed. AEs, SAEs, unanticipated problems, AEs related to the drug (possible, probable, or definite) and CTCAE Grade 3 and 4 AEs will be summarized overall. These summaries will include the number of events and the number and percentage of subjects with a given event. AEs will also be summarized by system organ class (SOC) and treatment group to identify AEs that occur at a higher frequency in subjects treated with ManNAc at different dose levels.

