**12.2. Monitoring and Reporting Plan**

AEs, protocol deviations, unanticipated problems (UP), and serious adverse events, are defined in NIH HRPP SOP 16 ("Reporting Requirements for Unanticipated Problems, AEs and Protocol Deviations", [Appendix G](#)). All AEs occurring from the time the informed consent is signed through the end of the follow-up period will be documented, recorded and reported.

An **adverse event (AE)** is any unfavorable and unintended sign (including a clinically significant abnormal laboratory finding, for example), symptom, or disease temporally associated with a study, use of a drug product or device whether or not considered related to the drug product or device.

**Serious unanticipated problems** that are at least possibly related to the research and suggest a greater risk or harm than previously known, **serious protocol deviations** will be reported to the IRB and CD (Clinical Director) as soon as possible but not more than 7 days if *serious* or 14 days if *not serious*, after the PI first learns of the event.

**Not serious unanticipated problems** will be reported to the IRB and CD as soon as possible but not more than 14 days after the PI first learns of the event.

**Protocol deviations** that represent non-compliance (see SOP 16A) will be reported to the IRB and CD within 7 days if serious and 14 days if not serious.

**Not serious protocol deviations** that do not represent non-compliance will be reported to the IRB as soon as possible but not more than 14 days after the PI first learns of the event part of the Continuing Review.

Anticipated deviations in the conduct of the protocol will not be reported to the IRB unless they occur at a rate greater than anticipated by the study team. Expected AEs will not be reported to the IRB unless they occur at a rate greater than that known to occur in GNE myopathy. If the rate of these events exceeds the rate expected by the study team, the events will be classified and reported as though they are unanticipated problems.

**Deaths** will be reported to the Clinical Director within 7 days after the PI first learns of the event.

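### Sections 12.1.1 and 12.2 apply different tests for when a laboratory abnormality is an AE, and Section 7.2.2 plans no graded laboratory summary, so the Grade 3-4 summary can depend on staff judgment

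*Combined protocol and SAP*

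**What the plan says.** **When a laboratory value is an AE.** Section 12.1.1 gives two routes.

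- Expected route: "A laboratory abnormality should be reported as an AE if it requires an intervention". The term is broad: "Interventions include, but are not limited to, discontinuation of treatment, dose reduction/delay, additional assessments, or concomitant treatment".
- Discretionary route: "any medically important laboratory abnormality may be reported as an AE at the discretion of the investigator". The protocol adds: "This could include a laboratory result for which there is no intervention, but the abnormal value suggests disease or organ toxicity".

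Neither route refers to a CTCAE grade. Section 12.2 defines an AE as an unfavorable and unintended sign, "including a clinically significant abnormal laboratory finding, for example". It sets no intervention condition and requires all AEs to be recorded and reported. Section 5.2.2 sends abnormal results judged not clinically significant to a progress note.

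**What is summarised.** Section 4.7 lists clinical laboratory tests next to AEs as a safety component, classified by CTCAE version 4.03. Section 7.2.2 lists all safety data and then summarises AEs, SAEs, unanticipated problems and drug-related AEs; for severity, "CTCAE Grade 3 and 4 AEs will be summarized overall". It names no laboratory grade, shift or change-from-baseline table. Section 7.1.1 gives general descriptive conventions without naming a laboratory analysis.

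**What the safety rules count.** In Table 6 the safety-profile column is mostly worded in AEs and SAEs. The decision column includes "Discontinue study if 2 subjects develop the same Grade 3 toxicity", which speaks of toxicity and does not define it.

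**The concern.** Safety and tolerability form the first primary objective (Section 2.1). Section 3.8.1 names six effects that may be seen in humans. Five are laboratory findings: anemia, albumin, BUN, transaminases and urinalysis. Section 3.8.2.2 adds triglycerides: "One subject in the study had Grade 3 hypertriglyceridemia". For such effects the measured value is the objective evidence, and it should reach a summary whatever anyone decided about it.

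As written, the same graded value can be an AE in one subject and a listing entry in another. The decision lies with staff who know the treatment, since Section 4.11 provides for no blinding. A reader of the final report could not tell whether a low Grade 3-4 count reflects few abnormal values or few values called AEs.

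**Working it through.** The plan states no figure to reproduce here: the reporting rule has no operating characteristic, and the sample size of 12 (Sections 4.2 and 7.3) comes from no formula. The check is mainly a comparison of text.

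**Step 1. Apply both definitions to one value.** Take a Grade 3 laboratory result that suggests organ toxicity, with no treatment change and no further test required.

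| Question | Section 12.1.1 | Section 12.2 |
|---|---|---|
| What is the test? | An intervention is required, or the investigator chooses | The finding is clinically significant |
| Must this value be recorded as an AE? | No, discretionary | Yes, if judged clinically significant |
| Does the CTCAE grade decide? | No | No |

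The sections disagree on a value judged clinically significant that needs no intervention. Both leave the decision to judgment.

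**Step 2. Follow the value into the analysis.** If it is called an AE, it enters the Grade 3-4 summary in Section 7.2.2. If not, it appears in a listing and in no summary that the section names.

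**Step 3. Size of one omission.** Input: N = 12. Section 7.2.2 reports the percentage of subjects with an event, so one subject contributes 1/12 = 0.083, or 8.3 percentage points, provided that subject has no other Grade 3-4 AE. If another such AE is already counted, the subject rate does not move and only the event count changes. Exact (Clopper-Pearson) 95% intervals:

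- 0 of 12: 0%, interval 0 to 26.5%.
- 1 of 12: 8.3%, interval 0.2 to 38.5%.

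**Step 4. Illustration for the two-subject rule, on assumed inputs.** Suppose, which the text does not establish, that the rule were run on AE reports alone. Let p be the true proportion of subjects with a given Grade 3 laboratory toxicity, c the share of such cases reported as AEs, and q = p × c. The documents give neither p nor c. Then

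P(at least 2 of 12) = 1 − (1 − q)^12 − 12q(1 − q)^11.

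For example, p = 0.10 and c = 0.5 give q = 0.05 and 1 − 0.540 − 0.341, about 0.118.

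| p | c = 1 | c = 0.75 | c = 0.5 |
|---|---|---|---|
| 5% | 0.118 | 0.072 | 0.035 |
| 10% | 0.341 | 0.226 | 0.118 |
| 20% | 0.725 | 0.557 | 0.341 |

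Under these assumptions, incomplete capture matters in a study this small. The table does not estimate what happened in this one.

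**The case against.** The best defence is that little can slip through. A value that requires even a repeat test meets Section 12.1.1, because additional assessments count as interventions. To escape both sections, a Grade 3-4 value must require no follow-up, be judged not clinically significant, and be passed over at discretion. All safety data are listed, and in 12 subjects a listing can be read line by line. Section 4.8 gives the SRC laboratory data, and Section 3.8.2.2 confirms that its review included them. The Grade 3 hypertriglyceridemia was graded, attributed and disclosed. Gastrointestinal effects, not laboratory ones, are described as the most prominent in the toxicology studies, and 8 of the 12 subjects had gastrointestinal tolerability issues or drug-related AEs.

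Most of this stands, and it rules out several stronger readings that a reader might infer:

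- *That a laboratory value is an AE only if someone intervened.* Section 12.2 says otherwise, and Section 12.1.1 does not say *only*.
- *That laboratory toxicity is left out of the primary safety result.* It is a separate safety component and is listed. What is missing is a named summary.
- *That the stopping rule ignores unreported values.* The two-subject wording refers to toxicity, so it is not clearly limited to AEs. Nor is it clear that it includes values not reported as AEs: the safety-profile column is mostly in AE terms, Section 12.3.1 bases cohort dose decisions on AE data, and the DSMB review in Section 12.3.2 covers AEs and SAEs.

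The defence does not remove the conflict between the two sections or supply a graded summary. One disclosed event shows that capture occurred once, not that the rules secure it.

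**Conclusion.** The point holds as an inconsistency and a gap in the analysis plan. Sections 12.1.1 and 12.2 differ on whether a clinically significant laboratory value needing no intervention must be recorded as an AE. Because Section 7.2.2 summarises only events, the Grade 3-4 result for a primary objective can depend on open-label judgment.

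The size is 8.3 percentage points per omitted subject, assuming a denominator of 12 and no other Grade 3-4 AE in that subject. It is not 8.3 points per event. How often this could occur is unknown, and the documents give no instance of a missed event. The class of values at risk is narrow because additional assessments count as interventions. The change is still worth making: it costs little and makes the graded laboratory result independent of AE reporting.

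**What to change.** 1. **Sections 12.1.1 and 12.2.** Reconcile them so that a single criterion governs when a laboratory abnormality is recorded as an AE.
2. **Section 7.2.2.** Add a table of worst on-treatment CTCAE grade against baseline grade, for each laboratory parameter that has CTCAE grades. Build it from the laboratory data already collected, not from the AE form, and include data from visits already completed.
3. **Table 6.** Reconcile the AE and toxicity wording so that it is clear whether graded laboratory values count. The content of the rule is for the sponsor and the SRC. Settle this together with item 1, since what is recorded as an AE feeds the AE-worded rows.

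Making every Grade 3 or higher value an AE automatically is not proposed. It would capture abnormalities unchanged from baseline. It would also feed the Table 6 row for any Grade 4 AE, whose listed decision is withdrawal, and so could change how often a safety rule is triggered.

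The cost is wording changes and one programmed table, with no new procedures or samples. Some shifts in the table will reflect the underlying muscle disease; showing baseline grade beside worst grade helps the reader judge them but does not remove them.

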#### **Definitely Related:**

- clear temporal association
- follows a known response pattern
- clear evidence to suggest a causal relationship
- there is no alternative etiology

#### **Probably Related:**

- temporal association
- follows a suspected response pattern (based on similar agents)

- a more likely alternative etiology unlikely

**Possibly Related:**

- temporal association
- evidence exists for alternative etiology

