**Unlikely Related**

- no clear temporal association

OR

- good evidence for a more likely alternative etiology

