**Not Related**

- no temporal association

OR

- definitely due to an alternative etiology

Note: Other factors (e.g., dechallenge, rechallenge) should also be considered for each causality category when appropriate. Causality assessment is based on available information at the time of the assessment of the AE. The investigator may revise the causality assessment as additional information becomes available.

Pregnancy: Pregnancy itself is not an AE. However, complications of pregnancies are AEs and may be SAEs. In the event of pregnancy the following steps will be taken:

- Discontinuation of the study agent
- Withdraw from the study but continue in follow up for safety
- Report to safety oversight committee - SRC and IRB
- Advise research subject to notify the obstetrician of study agent exposure
- Safety data will be collected until completion of the pregnancy

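### As worded, the causality criteria leave an unprecedented, otherwise unexplained event outside the drug-related set, and evidence for another cause brings it in

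*Combined protocol and SAP*

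**What the plan says.** Section 12.1.1 asks the investigator to judge causality by weighing factors listed under five categories:

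- **Definitely Related**: clear temporal association, an event that "follows a known response pattern", clear evidence of causation, and "there is no alternative etiology".
- **Probably Related**: temporal association, an event that "follows a suspected response pattern (based on similar agents", and "a more likely alternative etiology unlikely".
- **Possibly Related**: temporal association, and "evidence exists for alternative etiology".
- **Unlikely Related**: met either when the link in time is not clear or when there is "good evidence for a more likely alternative etiology".
- **Not Related**: met either when there is no link in time at all or when the event is "definitely due to an alternative etiology".

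A note after the list says that other factors, such as dechallenge and rechallenge, should be considered where appropriate, and that an assessment may be revised. No default category is given for an event that meets none of the five, and no order of precedence for an event that meets two.

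Section 7.2.2 summarises "AEs related to the drug (possible, probable, or definite". Relatedness also enters the counts in sections 4.8 and 4.9 and Table 6, follow-up after the final dose (12.1.1), reporting of serious unanticipated problems to the IRB (12.2) and the early DSMB review (12.3.2).

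**The concern.** An unexplained event that follows dosing would ordinarily be treated as at least possibly related. Here the lowest counted category requires positive evidence for some other cause, and the two higher ones require a precedent. The event with the fewest competing explanations but no precedent is therefore left out, while a weaker case with a competing explanation is counted.

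This matters because the safety of multiple doses is a primary objective (2.1). The earlier clinical studies described in section 3.5 gave single doses, and the repeated human use described before this trial was anecdotal and unsupervised. Few response patterns were established when the trial began, so a pattern requirement is weakest where detection matters most.

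The overlap between Possibly and Unlikely adds a second problem. The same event can be counted or not counted depending on which definition the investigator reads first.

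**Working it through.** The plan states no figure to reproduce; the check is one of logic.

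**Reading used.** Criteria within a category are joined by *and*, because only Unlikely and Not Related print *or*. A known pattern is taken to satisfy a suspected one. Probably is taken to allow no alternative or some evidence for one, but not good evidence for a more likely one. The causal-evidence criterion of Definitely is taken as met; this does not affect the result, because those events also meet Probably.

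**Grid.** Temporal association (none, present but not clear, clear) × response pattern (none, suspected, known) × alternative etiology (none, some evidence, good evidence for a more likely one, definite) = 3 × 3 × 4 = 36 profiles.

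**The key events, with no known or suspected pattern:**

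| Timing | Alternative etiology | Categories met | Counted in 7.2.2? |
|---|---|---|---|
| Clear | None | None of the five | No |
| Present, not clear | None | Unlikely | No |
| Clear | Some evidence | Possibly | Yes |
| Clear | Good evidence, more likely | Possibly and Unlikely | Ambiguous |

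Rows 1 and 3 show the reversal: the only change is added evidence for another cause, and the event moves from uncounted to counted.

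**Counts, taking the word *clear* in Unlikely literally.**

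- No category: 1 (row 1).
- Both a counted and a non-counted category: 17, made up as follows.
  - Timing not clear, some, good or definite alternative: 3 alternatives × 3 patterns = 9.
  - Timing not clear, no alternative, suspected or known pattern: 2.
  - Timing clear, good or definite alternative: 2 × 3 = 6.
  - 9 + 2 + 6 = 17.

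**Counts if the Unlikely timing criterion means no temporal association at all.**

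- No category: 2 (rows 1 and 2).
- Both kinds of category: 2 timings × 3 patterns × 2 alternatives (good, definite) = 12.

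**Effect of the fix, on the literal reading.** Rewording Possibly and giving Unlikely precedence for a well-supported, more likely alternative reduces unclassified profiles from 1 to 0 and double-classified ones from 17 to 6. The 6 have timing that is not clear and no or only some alternative evidence (2 × 3 patterns). Aligning the Unlikely timing criterion, so that timing sufficient for Possibly cannot also satisfy Unlikely, brings the 6 to 0.

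**Scale for one subject.** With 12 subjects, one subject moved in or out of the drug-related set changes a drug-related incidence by 1/12 = 8.3 percentage points. This shows sensitivity; it does not estimate actual error.

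**The case against.** The best defence is that 12.1.1 is guidance and not an algorithm. It asks the investigator to consider factors, no category prints *and*, and the closing note brings in dechallenge, rechallenge and later revision. Section 12.2.1 separately asks, for expedited reports, whether there is a reasonable possibility that the drug caused the event. Nothing tells an investigator to call an unexplained post-dose event unrelated. This stands in part: judgment may rescue individual events. But judgment without a default category or a tie-break makes the coding depend on the assessor.

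Second, much of the safety system ignores relatedness. Section 7.2.2 lists all safety data and summarises AEs overall and by system organ class. The first Cohort A escalation rule (4.8.1) looks at any serious AE, Table 6 acts on any Grade 4 AE, and all SAEs go to the FDA (12.2.1). The SRC reviews all AE data, and the DSMB reviews all AEs and SAEs yearly. This stands and limits the consequence.

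A reader might infer three stronger things that the documents do not support:

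- *Every novel, unexplained event goes unclassified.* On the literal wording, one whose timing is not clear meets Unlikely.
- *A new ManNAc toxicity would be declared unrelated or go unseen.* With clear timing the event is unclassified, which is different from unrelated, and it would still appear in the listings and overall summaries.
- *Events have been miscoded.* None is shown to have been. The one Grade 3 hypertriglyceridemia described in 3.8.2.2 was judged probably related.

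**Conclusion.** The defect holds as a fault in the written criteria. An event with no known or suspected pattern and no alternative cause falls outside the possible, probable or definite set whether its timing is clear (no category) or present but not clear (Unlikely). Evidence for another cause makes it meet Possibly. Separately, events with a temporal association and good evidence for a more likely cause meet both a counted and a non-counted category.

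The size is 1 unclassified and 17 double-classified profiles of 36, or 2 and 12 on the looser timing reading. These are counts of logical combinations, not expected frequencies, and they rest on reading each category's criteria jointly. The exclusion of the unprecedented, unexplained event from the counted set holds under both timing readings.

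The practical exposure is mainly non-serious Grade 1-3 events in the drug-related summary and in the counts of 4.8, 4.9 and Table 6, together with the relatedness-based SAE triggers and follow-up after the last dose. The change is worth making because the rule misorders events and costs little to correct.

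**What to change.** 1. Reword Possibly Related as: *temporal association, and either no alternative etiology is identified or one exists but is not more likely than study drug; no response pattern required.*
2. State that good evidence for a more likely alternative means Unlikely Related, not Possibly Related.
3. Align the first Unlikely criterion, for example *temporal association not reasonable*, so that an event cannot meet both Possibly and Unlikely on timing.
4. Re-check causality for AEs already coded Unlikely or Not Related with no alternative cause recorded.

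The cost is three wording changes and one listing review in a study planned for 12 subjects. The small downside is that a few more AEs may count as drug-related.
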